## ER-GP identification

During a Symptoms Clinic consultation an ER-GP may identify an AE or SAE through the participant's account of recent clinical events or through their expressed concerns. ER-GPs

<sup>1 E.g. Abdominal pain admission in a patient with Irritable Bowel Syndrome or a neurological admission in a patient with functional neurological symptoms.

will use their clinical experience to assess and manage changes in patients' clinical conditions, working within the policies of the study.

If the ER-GP has a concern for the mental distress of a participant they will administer the PHQ-9 to determine if the participant meets the threshold for an adverse event.

The ER-GP will be trained in what constitutes an AE and SAE.

### Health resource use data collection

Health resource use will be collected from medical notes by the research team after the final outcome assessments have been completed at 52 weeks. All health resource contacts will be collected at this time point, including GP appointments, out-patient appointments, accident and emergency attendance, in-patient events and service contact or attendance such as NHS 111 and out of hours or walk in centre.

Any of the above events which result in a hospital admission, and have not previously been identified through patient report or ER-GP identification will be reported as an SAE.

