# 7.5 Participant withdrawal, discontinuation and loss to follow up

Participants may withdraw from active participation in the study on request. Individuals withdrawn from the intervention will not be replaced and will be followed up for all outcomes, unless they specifically request to be withdrawn from follow up data collection. We will ask permission to collect their healthcare resource use from their GP practice at 52 weeks; participants will have the opportunity to opt out of this on withdrawal. The reason for withdrawal from the intervention/study, if known, will be recorded on a Case Report Form (CRF). However, data up to the time of consent withdrawal will be included in the data reported for the study.

If an enrolled patient is found to have a new clinical condition causing their symptoms, the ER-GP will report this to the usual care GP and CI. A decision about further study appointments will be discussed on an individual case basis; guided by the participants' choice as to whether they wish to continue attending the appointments. If a participant is withdrawn from the intervention on this basis follow up data will still be collected and included in the intention to treat analysis.

A participant will be considered lost to follow up if they do not return the participant completed outcome measures at 52 weeks after all reminder options have been utilised, according to the outcome data follow up guidance, ie. no response to telephone contact, reminder letter or email. If a participant does not respond to earlier follow up questionnaires (at 13 and 26 weeks) we will still approach at subsequent follow up time points.

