## Serious Adverse Event (SAE)

An SAE is an event that:

- (a) results in death;
- (b) is life-threatening\* (subject at immediate risk of death);
- (c) requires hospitalisation or prolongation of existing hospitalisation\*\*;
- (d) results in persistent or significant disability or incapacity;
- (e) consists of a congenital anomaly or birth defect
- (f) is otherwise considered medically significant by the investigator\*\*\*

\* 'life-threatening' in the definition of 'serious' refers to an event in which the patient was at risk of death at the time of the event; it does not refer to an event which hypothetically might have caused death if it were more severe.

\*\*Hospitalisation is defined as an inpatient admission, regardless of length of stay, even if the hospitalisation is a precautionary measure for continued observation. Hospitalisations for a pre-existing condition, including elective procedures that have not worsened, do not constitute an SAE.

\*\*\*Other important medical events that may not result in death, be life-threatening, or require hospitalisation may be considered a serious adverse event/experience when, based upon appropriate medical judgement, they may jeopardise the patient and may require medical or surgical intervention to prevent one of the outcomes listed in this definition.

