## **Expected SAEs**

Serious adverse events that are expected or have the potential to be experienced by the patient population: (a) diagnosis of cancer, (b) diagnosis of a serious medical condition, (c) admission to hospital with an exacerbation of persistent physical symptoms (d) self-harm (resulting in hospitalisation or otherwise meeting the definition of a serious adverse event); (e) suicide attempt; (f) death from suicide.

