### Participant Self-report

Self-report questionnaires will be collected at baseline, 13 weeks, 26 weeks and 52 weeks post randomisation. The PHQ-9 will identify exacerbation of mental distress and current suicidal thoughts. If a patient scores 3 on question 9 of the PHQ-9 at baseline then they will not be randomised in to the study and the suicide protocol will be triggered. This can be triggered at any point during the study if a score of 3 is identified and the event will be reported as an AE. The health resource use questionnaire will include questions about A&E attendance and hospital admissions.

Whilst it is unlikely that participants will report SAEs between data collection points they will be provided with contact details of the CTRU research team on which they can contact to inform them of an event.

Self-reported SAEs will be flagged to the Trial Manager (or delegated member of staff in the absence of the Trial Manager). The patient completed PHQ-9 and SAE data will be monitored by the CTRU research team to allow efficient identification and reporting of events. Where an event has been identified by the CTRU research team but more information is required they will contact the participant (by telephone in the first instance) to obtain more detailed information about the event.

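### The 52-week notes review names hospital admission as its only explicit SAE trigger, which is narrower than the protocol's own SAE definition, so deaths outside hospital and serious diagnoses without admission may go unreported, more so under usual care

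*Protocol*

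**What the plan says.** Protocol section 9.1 defines an SAE by six criteria. Admission is one. Others include an event that "results in death" and one that "is otherwise considered medically significant by the investigator". The list of expected SAEs opens with "a) diagnosis of cancer, (b) diagnosis of a serious medical condition" and ends with suicide attempt and death from suicide. None of these four items requires an admission. The self-harm item does carry a qualifier (hospitalisation, or meeting the SAE definition in another way), so the authors attached a condition where they wanted one.

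Section 9.2 gives three routes of identification: participant self-report, the ER-GP during clinic consultations, and the collection of health resource use from the notes. On the notes it says: "All health resource contacts will be collected at this time point, including GP appointments, out-patient appointments, accident and emergency attendance, in-patient events". The reporting rule that follows covers "Any of the above events which result in a hospital admission, and have not previously been identified through patient report or ER-GP identification". It names no other SAE criterion.

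On self-report, section 9.2 mentions the PHQ-9 and adds: "The health resource use questionnaire will include questions about A&E attendance and hospital admissions". Table 1 in section 7.4 places self-reported healthcare use at 26 and 52 weeks. If a new condition is found to explain an enrolled patient's symptoms, section 7.5 says that "the ER-GP will report this to the usual care GP and CI".

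**The concern.** The trial tests a clinic that explains persistent symptoms to patients whose symptoms are thought not to come from disease. A natural safety question is whether serious disease is missed or diagnosed late. To answer it, serious diagnoses and deaths must be found in the same way in both arms.

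Two of the three routes cannot secure this. Self-report depends on a reply, and the protocol allows for 25% loss to follow-up. The ER-GP route operates only in consultations that usual-care participants do not have. The notes review could restore the balance, because it is scheduled for both arms and needs no reply. Its stated SAE rule, however, is narrower than the definition it should serve. A reviewer who follows that sentence alone has no prompt to report a death at home or a cancer diagnosed in an outpatient clinic.

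Section 9.1 itself expects adverse events to be identified differently in the two arms. It uses this as a reason to limit non-serious AE collection and offers no matching remedy for SAEs.

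**Working it through.** The point rests on the text, so the sections are set side by side for a usual-care participant.

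| Event | SAE under 9.1? | Covered by the stated notes-review trigger? | Other stated route |
|---|---|---|---|
| Death outside hospital | Yes, criterion (a) | No | Cannot be self-reported |
| Cancer or other serious disease diagnosed without admission | Yes, expected SAEs (a) and (b) | No | None that asks; the participant may volunteer it |
| Suicide attempt, seen in A&E and discharged | Yes, expected SAE (e) | No | A&E question; self-harm recorded as an AE from the notes (9.1, item b) |
| Admission for a new illness | Yes, criterion (c) | Yes | Admission question |
| Admission for a pre-existing condition that has not worsened | No, excluded in 9.1 | Yes | Admission question |

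The first three rows show where the trigger is too narrow. The last row shows that the same sentence is also too broad.

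**Extent of the mismatch.** One of six SAE criteria serves as a trigger. Four of the six expected SAEs (a, b, e, f) have no admission condition. Many such events will still involve an admission, so the gap is the part that does not.

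**Difference between arms.** In the clinic arm the ER-GP is trained in what counts as an AE or SAE, can identify one in consultation, and passes a new condition to the CI. Usual care has no equivalent.

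**Illustrative bound.** The inputs are 188 per arm (section 8.1.2) and new disease in about 1 in 25 clinic cases (section 6.1.4).

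- Arm size check: 2 × (1.960 + 1.282)² × 5² / 2² = 131.4, so 132 per arm. Then 132 / 0.75 = 176, and 176 × 1.06 = 186.6 (or 176 / 0.94 = 187.2), consistent with the stated 188.
- Participants with newly recognised disease: 188 / 25 = 7.5 in the clinic arm, and 7.5 under usual care if the underlying rate is equal (assumption).
- The documents give no proportion admitted. Over an assumed range:

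| Assumed proportion admitted | Within the stated trigger | Outside it |
|---|---|---|
| 10% | 0.8 | 6.8 |
| 25% | 1.9 | 5.6 |
| 50% | 3.8 | 3.8 |
| 75% | 5.6 | 1.9 |

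The last column is an upper bound per arm. The 1 in 25 refers to any new disease, serious or not, and other routes may capture some cases.

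**The case against.** The strongest reply is that section 9.2 does not say that admissions are the only events to report. Section 9.1 defines an SAE whatever its source, and section 9.3 requires every identified SAE to go to the trials unit within a working day. A reviewer who reads of a death or a cancer and recognises it as an SAE is bound by that. This stands, and it limits the claim: such events are at risk of being missed, not certain to be. It does not remove the point. Section 9.3 acts once an event has been identified, and the only instruction on what the notes reviewer should treat as an SAE is the admission rule.

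Four stronger readings are tempting and are not supported.

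- A reader might infer that the notes are the only systematic source for usual care. They are not: questionnaires go to both arms at 13, 26 and 52 weeks, and the trials unit contacts participants for more detail where needed.
- A reader might infer that suicide attempts without admission are lost. Section 9.1 collects self-harm from the notes with no admission condition, and the questionnaire asks about A&E attendance. What is at risk is mainly the SAE label.
- A reader might take "after the final outcome assessments have been completed at 52 weeks" to mean that participants who died or did not respond are never reviewed. The wording concerns timing: section 7.4 puts the notes last because reading them may unblind the assessor, and section 7.5 provides for record collection after withdrawal, subject to opt-out. Deaths and non-response are not mentioned, so a clear statement is still worthwhile.
- A reader might turn the 7.5 per arm into a multiple, such as a two- to four-fold excess of events in the clinic arm. That would compare conditions known to the CI with SAE reports, which are different things, and would rest on an assumed admission rate. Clinic contact also covers only the early months; later events in that arm depend on the same routes as usual care.

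Nor is it right that the arms cannot be compared at all. The underlying contacts are collected identically in both. The weakness lies in which of them become SAE reports.

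**Conclusion.** The point holds as a contradiction between the notes-review rule in section 9.2 and the SAE definition in section 9.1. The one scheduled source that spans both arms without needing a participant's reply has a single explicit SAE trigger, and that trigger leaves out deaths outside hospital and serious diagnoses made without admission. Because the ER-GP route serves only clinic attenders, the risk of under-reporting is greater under usual care.

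The number of SAEs affected cannot be derived from the documents. The bound of about 7.5 participants per arm assumes the protocol's 1 in 25 applies to everyone allocated and equally to both arms, and it counts disease that may not be serious. The conclusion does not depend on it. This is more than missing detail, because the stated rule disagrees with the protocol's own definition. It should be corrected, and the correction is small.

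**What to change.** Replace the final sentence of the health resource use part of section 9.2 with wording to this effect: any event found in the notes between randomisation and 52 weeks that meets the SAE definition in section 9.1, and has not already been identified, is reported as an SAE in both arms. This includes death and the diagnoses and suicide-related events on the expected-SAE list, whether or not there was an admission. The section 9.1 exclusion for admissions for pre-existing conditions that have not worsened applies.

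State that the review also covers participants who died or did not return questionnaires, where consent allows. Reconcile the text with the self-harm item in section 9.1, so that it is clear when an event in the notes is an AE and when an SAE, and with the general reporting duty in section 9.3. Add matching fields for death and new serious diagnosis to the extraction form.

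The cost is slight, because the same notes are already read: a little more extraction time, and an SAE count that rises for events without admission and falls for admissions that section 9.1 excludes.

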# 9.1 Definitions

## Adverse event (AE)

A standard definition of an AE is "any untoward medical occurrence in a study participant".

The MSS3 patient population – who by definition have multiple symptoms and at least moderate healthcare use - are likely to experience many 'medical occurrences'. It is difficult to identify which medical occurrences are 'untoward' but fall short of the serious adverse event criteria. The multiple and complex symptoms of this population mean that the link of causality between the intervention and the event will be difficult to interpret. In addition, due

to the data collection methods employed in the trial, we anticipate differential identification of adverse events between arms, as those attending the symptoms clinics will be having regular contact with a GP over the first months of the trial. We expect any non-serious adverse events reported via participant-completed questionnaires or contained in GP records to be less reliable than those collected by the ER-GP and contain incomplete information.

For this study we therefore consider the collection of all non-serious adverse events both problematic and of limited utility. We will therefore only collect the following AEs: (a) significant exacerbation of mental distress defined as a PHQ-9 score of 20 or more and/or a score of 2 or 3 on question 9 (suicidality item), representing at least a 1 point score change (i.e a change from 2 to 3 from their previous measure)

(b) self-harm, which may be identified by the ER-GP during consultations or where volunteered by the participant to a member of the research team or through review of medical notes

(c) any emerging serious mental illness or substance use disorder identified after randomisation

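### The notes review in section 9.2 reports every newly found hospital admission as an SAE, although the SAE definition in section 9.1 excludes elective admissions and admissions for pre-existing conditions that have not worsened

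*Protocol*

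**What the plan says.** **The definition.** Section 9.1 makes hospitalisation one of the SAE criteria, counts any inpatient admission whatever its length, and then carves out an exception: "Hospitalisations for a pre-existing condition, including elective procedures that have not worsened, do not constitute an SAE". I read the condition about worsening as applying to the underlying condition as well as to the elective procedure.

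**Three detection routes (section 9.2).**

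- *Self-report, both arms.* "The health resource use questionnaire will include questions about A&E attendance and hospital admissions". Table 1 in section 7.4 places self-reported healthcare use at 26 and 52 weeks. The CTRU may telephone the participant if it needs more detail about an event.
- *ER-GP, clinic arm only.* "During a Symptoms Clinic consultation an ER-GP may identify an AE or SAE through the participant's account of recent clinical events". Also, "The ER-GP will be trained in what constitutes an AE and SAE".
- *Notes review, both arms.* This takes place after the 52-week assessments. "All health resource contacts will be collected at this time point, including GP appointments, out-patient appointments, accident and emergency attendance, in-patient events" and certain other contacts. Those that "result in a hospital admission, and have not previously been identified through patient report or ER-GP identification will be reported as an SAE".

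**What happens next.** Section 9.3 sends SAEs to the CTRU within one working day. It allows a report to go in before the full clinical assessment is available, and has the local PI and/or CI, with the ER-GP where relevant, assess relatedness and expectedness. SAEs then go into the periodic safety reports to the REC, TSC and DMEC.

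**The concern.** The same admission has two statuses. A planned inpatient procedure for a stable, long-standing condition is not an SAE under section 9.1, but becomes one under section 9.2 if the notes are where it is first seen. Whoever completes the record review cannot obey both rules.

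At stake is the meaning of the SAE count. It would mix events that meet the definition with events that the definition expressly rules out, in proportions that depend on how each admission came to light. Elective admissions are not among the expected SAEs listed in section 9.1, so they could also be carried forward as unexpected. The oversight bodies would see a raised count without being able to tell how much of it reflects the detection rule.

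A second question follows. One of the three routes exists in one arm only, so the over-count might not be the same in both arms.

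**Working it through.** No figure in the protocol is in dispute, so there is nothing to reproduce. The check is a comparison of the rules, followed by an illustration of scale.

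**Step 1: do the rules conflict?** Take an inpatient admission for an elective procedure, with no worsening, not reported by the participant and not mentioned to an ER-GP.

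| Rule | Result |
|---|---|
| 9.1, SAE definition | Not an SAE |
| 9.2, notes review | Reported as an SAE |
| 9.3, reporting procedures | Assessed for relatedness and expectedness; no stated check that it meets 9.1 |

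The first two rows contradict each other, and the third does not resolve them.

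**Step 2: does the conflict depend on the route?** Only the notes review has a rule that turns an admission into an SAE automatically. The ER-GP is trained in the definition, and the CTRU can obtain details of a self-reported event, so both of those routes leave room to apply the exclusion. The protocol does not say expressly that they do.

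**Step 3: how large could the over-count be?** The protocol gives no admission or capture rates, so every rate below is an assumption. Only the arm size of 188 comes from the protocol (section 8.1.2).

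- q = non-qualifying admissions per patient over 52 weeks, 5% to 20%
- s = share of these already identified by self-report, 30% to 90%

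Non-qualifying SAEs added by the notes review in one arm = 188 × q × (1 − s).

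- Low: 188 × 0.05 × 0.1 = 0.9
- Middle: 188 × 0.10 × 0.4 = 7.5
- High: 188 × 0.20 × 0.7 = 26.3

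If the notes review applied the section 9.1 exclusion, this quantity would be 0 in both arms.

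**Step 4: could it differ between arms?** Only if a non-qualifying admission that is mentioned to an ER-GP, and judged not to be an SAE, counts as already identified and so escapes the notes-review rule. Let e be the share of the remaining admissions that reach the ER-GP.

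- If such admissions do not escape the rule, the difference is 0.
- If they do, the difference is 188 × q × (1 − s) × e. With e assumed at 10% to 50%, this runs from 0.9 × 0.1 = 0.1 to 26.3 × 0.5 = 13.2 events. At middle values (e = 30%) it is 7.5 × 0.3 = 2.3.

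The protocol does not say which of the two readings applies, so this calculation cannot settle whether an imbalance exists.

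**The case against.** **The sections can be read together.** Section 9.1 defines the SAE for the whole of section 9. The sentence in 9.2 could then be a rule for capturing events and avoiding duplicates, with judgement to follow, and section 9.3 does foresee a report going in before the full clinical assessment. This is the best defence, and part of it stands: reporting first and assessing later is provided for. But the only assessments that 9.3 names are relatedness and expectedness, and the wording of 9.2 is unconditional. A reader has to supply the missing check.

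**The stronger reading does not hold.** A reader might infer that the rule inflates SAEs in usual care and so flatters the Symptoms Clinic on safety. The documents do not support that, for four reasons.

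- No section says that an admission which the ER-GP judges not to be an SAE is exempt from the later notes review. On a natural reading it has not been identified as an SAE and is still caught at 52 weeks, as it would be in usual care.
- Self-report covers admissions in both arms and comes before the notes review, which adds only what was missed.
- ER-GP contact is one initial consultation and up to three follow-ups, concentrated in the first months, while admissions accrue over 52 weeks.
- The sentence in section 9.1 that seems to help, "we anticipate differential identification of adverse events between arms, as those attending the symptoms clinics will be having regular contact with a GP", is part of the argument for not collecting all non-serious events. If anything, it points to more detection in the clinic arm.

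Nor do the documents show that planned admissions will be frequent. Section 9 speaks of regular healthcare use, referrals and investigational tests, and gives no inpatient rate.

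**Conclusion.** The contradiction between the SAE definition in 9.1 and the notes-review rule in 9.2 is explicit, and section 9.3 states no step that resolves it. Followed as written, the protocol can count as SAEs admissions that its own definition excludes, in both arms, and pass them to the REC, TSC and DMEC.

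The size is unknown. The illustrative range of about 1 to 26 extra events per arm rests wholly on assumed rates and shows only that the over-count need not be trivial. It also assumes that self-reported admissions are judged against the definition.

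A difference between arms is possible because the ER-GP route exists only in the clinic arm. Neither its direction nor its size can be established from the protocol, and it may be zero or negligible. The point should be put right as an inconsistency in what is recorded as an SAE, and not presented as a demonstrated safety bias.

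**What to change.** Reconcile sections 9.1, 9.2 and 9.3 so that one SAE definition applies whichever route brings an event to light. For example, replace the notes-review sentence in 9.2 with: *An admission found in the notes that has not already been reported will be assessed against the SAE definition in section 9.1, including its exclusion, and will be reported as an SAE only if it meets that definition.* Section 9.3 should name this check alongside relatedness and expectedness.

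Add one field to the health resource use CRF recording whether the admission was planned or for a pre-existing condition, and whether that condition had worsened. Without it, an analysis plan could not reliably separate these admissions afterwards.

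The cost is one sentence in 9.2, a few words in 9.3 and one CRF field. No participant's care changes, and the team avoids completing SAE forms for events that are not SAEs.
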